3.3.4. Time to Clinical Status Improvement

Additional analyses will evaluate the time to improvement of at least one point on the clinical status 8-point ordinal scale. That is, improvement will be defined as a decrease of at least one point on the 8-point scale compared to the baseline value (e.g. from 5 to 4; from 5 to 3) and the time to improvement will be defined as the elapsed time (in days) from randomization to the earliest day of observed improvement. Note that since clinical status assessments are recorded as defined in Section 4.3, the day that is being assessed (not necessarily the day the response is collected) will be used to determine the timing of events.

For analyses of this outcome, imputation of the clinical score may be performed following the rules described in Section 6.5.

Any subjects that are lost to follow-up or terminated early prior to an observed improvement will be censored at the day of their last observed assessment. Subjects who complete follow-up but do not experience improvement will be censored at the day of their Day 29 visit. All deaths that occur on or before Day 29 (and prior to any observed improvement) will be considered censored at 28 days.

An alternative definition of improvement will also be used where improvement will be defined as a decrease of at least two points on the 8-point scale compared to the baseline value (e.g. from 5 to 3; from 5 to 2). The timing and censoring definitions will follow similarly to the above.

3.3.5. Time to Discharge or NEWS of ≤ 2

The time to discharge or NEWS of ≤ 2 will be defined as the elapsed time (in days) from baseline to the earliest day at which either of the following occur:

- Discharge from hospital, unless discharged to hospital or end-of-life care.
- Reported NEWS of ≤ 2 which is maintained for 24 hours

For the latter bullet, to meet this criterion, scores of ≤ 2 must be reported on consecutive study visits. The timing of the event will be set to the day of the second assessment. Subjects who enroll with a baseline NEWS of ≤ 2 must be discharged from the hospital to meet this endpoint.

All deaths or discharge to hospice or other end-of-life care that occur before discharge or before an observed NEWS of ≤ 2 will be considered censored at 28 days.

3.3.6. Days of Non-invasive ventilation/high-flow oxygen

Non-invasive ventilation/high flow-oxygen days will be defined as the number of days where the clinical status score is equal to 6. The Post-Discharge Supplemental Oxygen CRF questions regarding days of non-invasive ventilation or high-flow oxygen will be used for any time period the subject is not hospitalized at the study hospital. The total number of days will be the sum of all reported days, regardless of whether the days occur consecutively or in disjoint intervals. See Section 6.5 for the plan for handling subjects who do not have data through Day 29 or die prior to Day 29.

3.3.7. Days of Invasive Mechanical Ventilation/ECMO

Invasive Mechanical Ventilator / ECMO days will be defined as the number of days where the clinical status score is equal to 7. The Post-Discharge Supplemental Oxygen CRF questions regarding days of ECMO or invasive ventilation will be used for any time period the subject is not hospitalized at the study hospital. The total number of days will be the sum of all reported days, regardless of whether the days occur consecutively or in disjoint intervals. See Section 6.5 for the plan for handling subjects who do not have data through Day 29 or die prior to Day 29.

3.3.8. Days of Oxygen

Oxygen days will be defined as the number of days where the clinical status score is equal to 5, 6, or 7. The Post-Discharge Supplemental Oxygen CRF question regarding days of oxygenation (including ECMO, invasive ventilation, non-invasive ventilation, high-flow oxygen devices, and all other oxygen delivery devices) will be used for any time period the subject is not hospitalized at the study hospital. The total number of days will be the sum of all reported days, regardless of whether the days occur consecutively or in disjoint intervals. See Section 6.5 for the plan for handling subjects who do not have data through Day 29 or die prior to Day 29.

3.3.9. Days of Hospitalization

Duration (in days) of hospitalization will be defined as the number of days subject is hospitalized for COVID-19-related reasons starting from the date of randomization. It will be calculated as the total number of days hospitalized, including readmissions for COVID-19-related reasons. See Section 6.5 for the plan for handling subjects who do not have data through Day 29 or die prior to Day 29.

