
 ○ Non-invasive ventilation/high flow oxygen: 
 ▪ Non-invasive ventilation/high flow oxygen use up to Day 29. ▪ Incidence and duration of new non-invasive ventilation or high flow oxygen use during the study. 	
 ● Days of non-invasive ventilation/high flow oxygen (if applicable) up to Day 29

 ○ Invasive Mechanical Ventilation / extracorporeal membrane oxygenation (ECMO): 
 ▪ Ventilator / ECMO use up to Day 29. ▪ Incidence and duration of new mechanical ventilation or ECMO use during the study. 	
 ● Days of invasive mechanical ventilation/ECMO (if applicable) up to Day 29.

 ● Hospitalization 
 ○ Duration of hospitalization (days). 	
 ● Days of hospitalization up to Day 29

 ● Mortality 
 ○ 14-day mortality ○ 28-day mortality 	
 ● Date and cause of death (if applicable)

OBJECTIVES	ENDPOINTS (OUTCOME MEASURES)

 Laboratory efficacy: 
 d-dimer, and C-reactive protein (CRP) over time 	
 d-dimer, CRP on Day 1; Days 3, 5, 8, and 11 (while hospitalized); and Days 15 and 29 (if attends in-person visit or still hospitalized).

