7.4 Readmission

If a subject is discharged from the hospital and then readmitted prior to Day 11, they may be given the remainder of the remdesivir infusions and if prior to Day 8, they may be given the remainder of the subcutaneous injections. If the subject did not withdraw his/her consent to participate in the study, there is no need to reconsent upon readmission to the study hospital. However, the site will need to inform them that since he/she was readmitted, study product administration will resume and confirm that they still agree to receive study product.

The natural history of COVID-19 and its impact on pre-existing medical conditions is not completely understood. Because of this, all readmissions, regardless of reason, should be documented and the subject should get daily clinical status assessments (i.e., ordinal scale and NEWS) and other procedures done as per the SOA upon readmission. If the subject is re-admitted with diminished mental capacity, the site should discuss continued study participation with a LAR.

The study team will need to notify the study pharmacist of the readmission. The subject will not get the doses that they missed after being discharged. Upon readmission, the subject will get maintenance doses of infusion only since they already received the loading dose of the study product infusion on Day 1. No study product infusions should be given past Day 10. No subcutaneous injection should be given past Day 7. For all data collection procedures required for those readmitted, please see the MOP.

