3. STUDY OBJECTIVES AND ENDPOINTS

3.1. Study Objectives

Primary Objective

To evaluate the clinical efficacy, as assessed by time to recovery, of interferon beta-1a + remdesivir as compared to the placebo + remdesivir for patients with baseline ordinal score 4, 5, and 6.

Secondary Objectives

The key secondary objectives are

- To evaluate the clinical efficacy of interferon beta-1a + remdesivir relative to placebo + remdesivir in adults hospitalized with COVID-19 according to clinical status (8-point ordinal clinical scale) at Day 15 for patients with baseline ordinal score 4 and 5.
- To evaluate the clinical efficacy of interferon beta-1a + remdesivir compared to placebo + remdesivir, as assessed by time to recovery for patients with a baseline ordinal score of 4 and 5.

The other secondary objectives (by baseline severity [4 or 5] vs 6) are to:

1. Evaluate clinical efficacy of interferon beta-1a + remdesivir as compared placebo + remdesivir as assessed by:
 - Clinical Severity
 - 8-Point Clinical Status Ordinal scale:
 - Time to an improvement of one category and two categories from Day 1 (baseline) on the clinical status 8-point ordinal scale.
 - Subject clinical status using 8-point ordinal scale at Days 3, 5, 8, 11, 15, 22, and 29.
 - Mean change in the clinical status 8-point ordinal scale from Day 1 to Days 3, 5, 8, 11, 15, 22, and 29.
 - National Early Warning Score (NEWS):
 - Time to discharge or to a NEWS of ≤ 2 and maintained for 24 hours, whichever occurs first.
 - Change from Day 1 to Days 3, 5, 8, 11, 15, and 29 in NEWS.
 - Oxygenation:
 - Oxygenation use up to Day 29.
 - Incidence and duration of new oxygen use through Day 29.
 - Non-invasive ventilation/high flow oxygen:
 - Non-invasive ventilation/high flow oxygen use up to Day 29.

- Incidence and duration of new non-invasive ventilation or high flow oxygen use through Day 29.
- Invasive Mechanical Ventilation / extracorporeal membrane oxygenation (ECMO):
 - Ventilator/ECMO use up to Day 29.
 - Incidence and duration of new mechanical ventilation or ECMO use through Day 29.
- Hospitalization
 - Duration of hospitalization (in days) through Day 29.
- Mortality
 - 14-day mortality.
 - 28-day mortality.
- Laboratory Efficacy:
 - d-dimer, and C-reactive protein (CRP) over time

2. Evaluate the safety of interferon beta-1a + remdesivir through 28 days of follow-up as compared to the placebo + remdesivir as assessed overall, and by baseline ordinal scale category (4 or 5 vs. 6) by:

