3.2. Endpoints

Primary Endpoint

Time to recovery, where recovery is defined as clinical status in states 1, 2, or 3 of the 8-point ordinal scale, through Day 29 (+6).

- Clinical status of a subject (8-point ordinal scale) is defined below:
 8. Death;
 7. Hospitalized, on invasive mechanical ventilation or ECMO;
 6. Hospitalized, on non-invasive ventilation or high flow oxygen devices;
 5. Hospitalized, requiring supplemental oxygen;
 4. Hospitalized, not requiring supplemental oxygen - requiring ongoing medical care (COVID-19 related or otherwise);
 3. Hospitalized, not requiring supplemental oxygen - no longer requiring ongoing medical care;
 2. Not hospitalized, but new or increased limitation on activities and/or requiring new or increased home oxygen;
 1. Not hospitalized, no limitations on activities

Secondary Endpoints

The key secondary endpoints are:

- Clinical status (8-point ordinal scale) on Day 15.
- Time to recovery, where recovery is defined as clinical status in states 1, 2, or 3 of the 8-point ordinal scale, through Day 29 (+6).

The other secondary endpoints are:

- Ordinal outcome assessed while hospitalized (Days 3, 5, 8, 11) and on Days 15, 22, and 29.
- NEWS assessed daily while hospitalized (Days 3, 5, 8, 11) and on Days 15 and 29.
- Days of supplemental oxygen (if applicable).
- Days of non-invasive ventilation/high-flow oxygen (if applicable).
- Days of invasive mechanical ventilation/ECMO (if applicable).
- Days of hospitalization.
- Date and cause of death (if applicable).
- D-dimer and CRP on Day 1, while hospitalized (Days 3, 5, 8, 11), and on Days 15 and 29.
- SAEs.
- Grade 3 and 4 adverse events

- WBC with differentials, hemoglobin, platelets, creatinine, total bilirubin, ALT, AST, INR, d-dimer, and CRP on Day 1; Days 3, 5, 8, and 11 (while hospitalized); and Days 15 and 29 (if attends in-person visit or still hospitalized).

Exploratory Endpoints (not described in this SAP)

- Qualitative and quantitative polymerase chain reaction PCR for SARS-CoV-2 in OP swab on Day 1; Days 3, 5, 8, and 11 (while hospitalized); and Days 15 and 29 (if attends in-person visit or still hospitalized).
- Deep sequencing of the SARS-CoV-2 virus for those subjects with sustained vial shedding
- Qualitative and quantitative PCR for SARS-CoV-2 in blood on Day 1; Days 3, 5, 8, and 11 (while hospitalized).

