The original (as-classified by the site) ordinal scores will be used as the primary scoring method for analyses. The following modified ordinal scale will be used in sensitivity analysis of select outcomes:

8. Death;
7. Hospitalized, on invasive mechanical ventilation or ECMO;
6. Hospitalized, on non-invasive ventilation or high flow oxygen devices at oxygen flow rate greater than 15L/min;
5. Hospitalized, requiring supplemental oxygen or high flow oxygen devices at oxygen flow rate less than or equal to 15L/min;
4. Hospitalized, not requiring supplemental oxygen - requiring ongoing medical care (COVID-19 related or otherwise);
3. Hospitalized, not requiring supplemental oxygen - no longer requiring ongoing medical care;
2. Not hospitalized, but new or increased limitation on activities and/or requiring new or increased home oxygen;
1. Not hospitalized, no limitations on activities.

This scale will be denoted as the “Modified Oxygen Use” ordinal scale.

NEWS has demonstrated an ability to discriminate subjects at risk of poor outcomes. This score is based on 7 clinical parameters (see Section 8.1.2.3 in Appendix C of the study protocol). This should be evaluated at the first assessment of a given study day and prior to administration of study product. The 7 parameters can be obtained from the hospital chart using the last measurement prior to the time of assessment and a numeric score given for each parameter (e.g., a RR of 9 is one point, oxygen saturation of 92 is two points). This is recorded for the day obtained. i.e., on Day N, the Day N score is obtained and recorded as the Day N score.

Oxygenation, Non-invasive ventilation/high flow oxygen, Invasive Mechanical Ventilation / extracorporeal membrane oxygenation (ECMO), hospitalization and mortality will be assessed using results of the 8-point ordinal scale and post discharge eCRF questions.

Safety will be assessed by the following:

- Cumulative incidence of serious adverse events (SAEs) through 28 days of follow-up.
- Cumulative incidence of Grade 3 and 4 AEs.
- Discontinuation or temporary suspension of study product administration (for any reason).
- Changes in white cell count, hemoglobin, platelets, creatinine, total bilirubin, ALT, AST, and INR, d-dimer, C-reactive protein over time. Note D-dimer and CRP are not graded.

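### The SAP counts hospital days by COVID-19 cause, and so omits non-COVID readmissions, although the protocol endpoint carries no cause restriction

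*SAP*

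**What the plan says.** Protocol Appendix C section 3 lists duration of hospitalization among the additional secondary efficacy objectives and gives the endpoint as "Days of hospitalization up to Day 29". The SAP repeats it without qualification, as "Duration of hospitalization (in days) through Day 29" in section 3.1 and "Days of hospitalization" in section 3.2.

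The derivation in SAP section 3.3.9 differs. Its first sentence reads "Duration (in days) of hospitalization will be defined as the number of days subject is hospitalized for COVID-19-related reasons", counted from randomization. Its second reads "It will be calculated as the total number of days hospitalized, including readmissions for COVID-19-related reasons".

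Other passages bear on how this would work:

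- SAP section 4.3 names the data source: "hospitalization and mortality will be assessed using results of the 8-point ordinal scale and post discharge eCRF questions".
- Protocol Appendix C section 7.4 requires that "all readmissions, regardless of reason, should be documented", with daily clinical status on readmission. Its stated reason is that the effect of COVID-19 on pre-existing conditions is not fully understood.
- SAP section 6.5 sets the variable to 28 days for any death in hospital, whatever its cause. It assumes no readmission when a discharged subject has no further hospitalization data.
- SAP section 8.2.9 and Table 42 summarize the variable by medians and quartiles, and report readmittance incidence separately.

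**The concern.** The variable to be analysed is not the endpoint that the protocol states. A readmission judged to be for something other than COVID-19 contributes nothing. That can include a reaction to study drug: the injection-halting list in Appendix C section 7.1.1.2 names seizures not attributable to COVID-19 and thrombotic microangiopathy attributed to interferon. An efficacy duration that leaves out readmissions the treatment may have caused is hard to interpret as time in hospital.

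The filter also needs a judgement, made after randomization, about why the patient was in hospital. I found no criterion, assessor or adjudication step for that judgement in this variable. For time to recovery, by contrast, SAP section 3.3.2 names who reviews special cases and what data they use.

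**Working it through.** The documents give no sample size, power, rate or standard deviation for this endpoint, so there is no plan figure to reproduce. The check is a comparison of texts, followed by a sizing that rests on assumptions.

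**Step 1. The definitions side by side.**

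| Place | Cause restriction |
|---|---|
| Protocol Appendix C section 3, objective and endpoint | none |
| SAP 3.1, objective | none |
| SAP 3.2, endpoint list | none |
| SAP 3.3.9, sentence 1 | all days must be COVID-19-related |
| SAP 3.3.9, sentence 2 | stated for readmissions only |
| SAP 3.3.6 to 3.3.8, ventilation and oxygen days | none; days counted by score |
| SAP 6.5, death in hospital | none; 28 days |
| SAP 8.2.9 and Table 42, readmittance incidence | none stated |

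**Step 2. What 3.3.9 does with each kind of day.**

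| Kind of day | Sentence 1 | Sentence 2, natural reading |
|---|---|---|
| Index stay, COVID-19-related | counted | counted |
| Index stay, other cause | not counted | counted |
| Readmission, COVID-19-related | counted | counted |
| Readmission, other cause | not counted | not counted |

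The last row is settled: both sentences omit it. The second row is not: the sentences conflict. The ordinal scale does not resolve the conflict, because it does not separate the cause of a stay; its category 4 covers ongoing care whether or not it is for COVID-19. One inconsistency follows. A survivor readmitted for another cause and needing oxygen adds oxygen days under 3.3.8 but no hospital days under 3.3.9.

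**Step 3. Size, by assumption.** Let a share r of subjects have L extra non-COVID days. Before any cap at 28 days, leaving them out lowers the mean by r × L:

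- 0.02 × 4 = 0.08 days
- 0.04 × 4 = 0.16 days
- 0.10 × 8 = 0.80 days

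The mean is not the planned summary, so the quantiles matter more. At most a share r of subjects have a longer total under all-cause counting, so for any q

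P(all-cause ≤ q) ≥ P(restricted ≤ q) − r.

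Taking q as the restricted quantile at 0.50 + r makes the right side at least 0.50. The all-cause median therefore lies no higher than the restricted (50 + 100r)th percentile: the 52nd for r = 2%, the 54th for 4%, the 60th for 10%. The same argument for the third quartile gives the 77th, 79th and 85th. These bounds hold whatever the length of the extra stays.

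A simulation with assumed skewed stays (log-normal, median 5 or 8 days, log-scale SD 0.7, rounded up to whole days, capped at 28), r of 2% to 10% and L of 4 or 8 days gave:

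| Assumed median | Fall in mean | Median, restricted → all-cause | Third quartile, restricted → all-cause |
|---|---|---|---|
| 5 days | 0.08 to 0.79 | 5 → 6 | 8 → 9 or 10 |
| 8 days | 0.08 to 0.75 | 9 → 9 | 13 → 13 to 15 |

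The one-day step in the median should not be over-read. An assumed median of exactly 5 or 8 days sits on a whole-day boundary, where a very small change can tip the rounded value.

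**Step 4. Between-arm effect.** On the mean scale, the difference between arms changes by r₁L₁ − r₀L₀. With 4-day stays:

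- 4% against 4% gives 0.16 − 0.16 = 0
- 4% against 2% gives 0.16 − 0.08 = 0.08 days
- 4% against 0% gives 0.16 − 0 = 0.16 days

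**The case against.** The strongest reply is that this matters little and may be deliberate.

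- **Role of the endpoint.** It is one of the other secondary endpoints, summarized descriptively. It is outside the gated tests of SAP section 6.8 and has no p-value in Table 42. This stands.
- **Drug-related stays remain visible.** Prolonged hospitalization is an SAE criterion, and Appendix C section 8.3.1 makes readmission for a worsening medical condition an SAE. SAE rates are compared by arm and enter the safety composite. This stands, but it does not make the efficacy variable match its definition.
- **A known convention.** The recovery sensitivity analysis in SAP section 3.3.2 also singles out readmission for COVID-19. That supports intent, but there the restriction belongs to a sensitivity analysis; here it defines the main variable, and no reason is given.
- **Attribution may be governed elsewhere.** The MOP covers readmission data, and Appendix C section 9.3 lets a committee that includes the blinded statisticians review endpoints. The MOP is not available here, so the fair statement is that the protocol and SAP state no rule.
- **Section 7.4 is about documentation.** It does not define this endpoint. This is correct; it shows only that all-cause readmissions are meant to be recorded.
- **Blinding.** The injections are blinded, which makes differential attribution less likely. It does not prevent loss of days where non-COVID stays truly differ by arm.

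Three stronger readings are tempting and should be set aside. A reader might infer that index-stay days prolonged by toxicity are certainly dropped; sentence 2 of 3.3.9 and the ordinal scale leave that open. A reader might infer that days are lost from the interferon arm only; comorbid illness and remdesivir reactions can occur in both arms, and the filter applies to both. A reader might infer that the readmission percentage in Table 42 is cut as well; neither section 8.2.9 nor the table shell states a cause filter.

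**Conclusion.** The mismatch is real and rests on the text alone: SAP 3.3.9 restricts by cause an endpoint that the protocol and the SAP's own objectives and endpoint list leave unrestricted. Non-COVID readmissions, including those for drug reactions, add no days in either arm. The treatment of index-stay days is ambiguous, and neither document states how cause is to be judged.

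The consequence is probably small. Under the assumed 2% to 10% of subjects with 4 to 8 extra days, the mean falls by about 0.1 to 0.8 days. In the simulation the median moved by 0 to 1 day and the third quartile by 0 to 2 days. None of these inputs comes from the documents. Bias between arms requires a real difference in non-COVID stays or in how they are attributed, and the documents show neither. No powered conclusion depends on this endpoint. It is a definition that should be corrected, not a threat to the trial's main result.

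**What to change.** Rewrite SAP 3.3.9 so that the main variable is the number of days in hospital for any cause from randomization through Day 29, adding the index stay and every readmission. One definition should replace the two conflicting sentences. Keep COVID-19-related days as a supporting summary, with a written rule stating who judges cause, on what data, and blind to treatment. State in Table 42 that readmittance is counted for any cause, if that is the intention.

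The cost is a short SAP edit, one extra derived variable, and footnotes to Tables 42 to 44. There are two drawbacks. Readmissions unrelated to study drug, including the social ones that Appendix C section 8.3.1 does not treat as SAEs, will also count. Dates may be less complete for stays elsewhere: Appendix C section 5.6.2 expects some readmissions to other hospitals, phone visits collect only a few items, and the section 6.5 rule treats missing post-discharge data as no readmission. The number of subjects with incomplete readmission dates should be reported beside the result.
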